### **3.11. Visit Windows**

It is expected that all visits should occur according to the protocol schedule. All data will be tabulated per the evaluation visit as recorded on the eCRF even if the assessment is outside of the visit window. In data listings, the relative day of all dates will be presented.

### **3.12. Interim Analyses**

In accordance with the Simon's two-stage optimal design of Part 1, there will be a preliminary assessment of efficacy for each cohort after the first 8 patients enrolled in that cohort have 6-month data available to assess DCR. Note that this initial analysis for a cohort may take place sooner than when the 8th patient has available data, should there be 3 or more disease control achievers after fewer than 8 patients are enrolled. Should the trial be terminated at the first stage, all efficacy and safety analyses as noted above will be performed. Patient enrollment into the trial will continue while the first stage analysis is being conducted.

### **3.13. Final Analyses**

The final analysis of the primary endpoint DCR for each cohort will take place after the target number of patients evaluable for DCR has been reached. Additional data summarization may take place after all available survival data are collected, or after Sponsor decision, as appropriate.

## 4. STUDY ANALYSES

### 4.1. Patient Disposition

[figure not shown]
Patient disposition will be tabulated and presented separately by cohort and overall for Part 1 and by schedule and overall for Part 2. It will include the number enrolled, the number in each patient population for analysis, the number who discontinued treatment and the primary reason for discontinuation, the number who completed or withdrew from the study and primary reason for study withdrawal.

The EOT Visit will occur  $\leq 14$  days after the patient receives their last dose of study treatment. A Safety Follow-up Call/Visit will be performed 30 days (+7 days) after last dose of study treatment. Follow-up ends when the patient has either completed that 30-day follow-up, withdrawn consent, been withdrawn by the Investigator, died, or been lost to follow-up. The end of study (EOS) will occur upon completion of the 30-day follow-up period for the last patient treated, or when Karyopharm has decided to end the study. Reason for treatment and study discontinuation will be recorded on the eCRF.

A by-patient data listing of study completion information including the reason for study withdrawal, if available, will be presented. By-patient listings of inclusion/exclusion criteria not met and follow-up visit survival status will also be presented.

#### Relevant Output

CCI

### 4.2. Demographics, Baseline Characteristics, and Medical History

Demographics, baseline characteristics, and medical history will be summarized and presented by cohort and overall for Part 1 and by schedule and overall for Part 2. Age at date of informed consent, height, weight, and BSA will be summarized using descriptive statistics (number of patients, mean, standard deviation, median, minimum, and maximum). The number and percentage of patients in each gender, ethnicity and race category will be presented. BSA will be presented using the Dubois and Dubois formula, where  $BSA = 0.007184 \times \text{Height (cm)}^{0.725} \times \text{Weight (kg)}^{0.425}$  (Dubois and Dubois, 1916).

Baseline characteristics include: Eastern Cooperative Oncology Group (ECOG) performance status; duration from initial diagnosis; response to previous therapy (Y/N).

[figure not shown]
Medical history will be summarized by System Organ Class (SOC) and Preferred Term. Medical history including baseline symptoms as well as a detailed history of the patient's disease, prior cancer therapies (including start and stop dates), PD during or after prior therapy, as well as discontinuations due to intolerability.

Disease history will include stage at initial diagnosis, primary tumor location, carcinoma subtype, whether at least one recurrence/relapse has been recorded, stage at most recent recurrence/relapse, and whether there are any current metastatic sites of cancer. Time since initial diagnosis, time since initial diagnosis to first recurrence/relapse, and time since most recent recurrent/relapse, will be summarized in months using descriptive statistics.

Prior treatments will include number and percentage of patients with prior radiation therapy (including setting and best overall response of most recent prior therapy), prior antineoplastic therapy (including best overall response and whether disease progressed during or after therapy of most recent prior therapy), and prior surgery type. Number of prior surgeries will be summarized.

Demographic, baseline, and medical history data, including previous antineoplastic therapies, previous radiation therapies, previous surgeries, tumor diagnosis, and disease-related toxicities from prior therapies and pregnancy test results for each patient will be provided in data listings.

#### Relevant Output

### **4.3. Efficacy Evaluation**

Efficacy analyses will be conducted using both the mITT and PP populations. Select secondary endpoints will be presented on the mITT extended population and the GCIG evaluable population as described below.

#### 4.3.2. Secondary Efficacy Analyses

All secondary efficacy analyses will be performed for the pooled data from both Simon stages, so no presentation of results for the first stage of the study is planned.

1. Response to therapy per RECIST v1.1: response for patients in each cohort will be determined by ORR, defined as either CR or PR using RECIST v1.1, calculated as a proportion and including a two-sided 95% CI for that cohort. In addition, to assist in evaluating the evidence of efficacy, a lower one-sided 90% CI for ORR will be calculated for each cohort in Part 1, and a two-sided 80% CI for ORR will be calculated for each schedule in Part 2. DOR will be also calculated from the date of first documented occurrence of response (CR or PR) until the date of documented progression, or last disease assessment, should progression not have occurred. The analysis of DOR will be based on the KM method for estimation of summary statistics, and include the 25th, 50th (median), and 75th percentiles and associated 95% CIs.
2. Response to therapy per GCIG response criteria (RECIST v1.1 and CA-125): response for patients in the ovarian cohort (Part 1 and Part 2) will also be assessed for DCR, Duration of SD, ORR, and DOR, as described above, using the GCIG response criteria. Number and frequency of patients in the ovarian cancer cohort who can be assessed using the GCIG response criteria will be presented. This analysis will be performed on the GCIG Efficacy Population only. In addition, a subset analysis for each endpoint will be conducted on the subgroup of patients with an initial CA-125 level of at least twice the upper limit of the reference range.

For the time-to-event endpoints (duration of SD and DOR), date of first response will be the first of response or progression per CA-125 or RECIST v1.1, whichever occurs first. Patients without documented progression will be censored at the day of their last evaluable disease assessment, either per RECIST or CA-125.

3. **PFS:** PFS for patients in each cohort will be calculated from the date of start of study therapy to the date of progression based on RECIST 1.1, or date of death due to any cause should progression not have occurred. Patients who do not have documented PD or drop out prior to study end will be censored at the day they were last known to be progression-free (i.e. day of their last evaluable disease assessment). The analysis of PFS for patients in each cohort will be based on the KM method for estimation of summary statistics, and include the 25th, 50th (median), and 75th percentiles and associated 95% CIs.

In addition to being performed on the mITT and PP populations, there will be three additional PFS analyses:

- a. As described above, but performed on the mITT extended population (i.e. including patients with non-measurable disease per RECIST at baseline).
  - b. PFS will also be presented with progression defined per GCIG response criteria (RECIST 1.1 and CA-125). PFS for patients in each cohort will be calculated from the date of start of study therapy to the date of progression based on RECIST 1.1 or CA-125, whichever occurs first, or date of death due to any cause should either type of PD not have occurred. Patients who do not have documented PD will be censored at the day they were last known to be progression-free (i.e. day of their last evaluable disease assessment, either per RECIST or CA-125). This analysis will be performed on the GCIG efficacy population only.
  - c. An additional sensitivity analysis may be performed that includes clinical progression (not documented per RECIST) as an event for PFS. For this analysis, PFS for patients in each cohort will be calculated from the date of start of study therapy to the date of progression based on RECIST 1.1 or date of clinical progression identified by the Investigator, whichever occurs first, or date of death due to any cause should either type of PD not have occurred. Patients who do not have documented PD or drop out prior to study end will be censored at the day they were last known to be progression-free (i.e. day of their last evaluable disease assessment per RECIST). This analysis will be performed on the mITT population.
4. **OS:** OS for patients in each cohort will be calculated from the date of start of study therapy to the date of death due to any cause. Patients who are alive at the time of the analysis or are lost to follow-up will be censored at the day they were last known to be alive. The analysis of OS for patients in each cohort will be based on the KM method for estimation of summary statistics, and include the 25th, 50th (median), and 75th percentiles and associated 95% CIs. OS rate at 12 and 24 months (OS12 and OS24) will also be presented for each cohort, determined from the KM estimate at 12 and 24 months. In addition to being performed on the mITT and PP populations, OS will also be performed on the mITT extended population.

5. QoL: QoL will be evaluated for patients in each cohort, and for all study patients combined by EORTC QLQ-C30 after 6 and 12 weeks of treatment and approximately every 8 weeks thereafter. The EORTC QLQ-C30 questionnaire has 30 general questions, and an additional cohort-specific set of 24 (for cervical and endometrial cancer) (CX24, EN24) or 28 (for ovarian cancer) questions (OV28). Each question is scored using a scale of 1 to 4, representing answers of Not at All, A Little, Quite a Bit, Very much; with the exception of the items contributing to the global health status, which are scored on a scale of 1 to 7, representing a range of Very Poor to Excellent.

The analysis will be performed on the sub-score of the initial (general) 30 questions of the EORTC QLQ-C30, and separately for the cohort-specific sub-score totals, as described in the EORTC QLQ-C30 Scoring Manual and in Section 4.3.5. All of the scales and single-item measures range in score from 0 to 100, where a high score represents a higher response level. A high score for a functional scale represents a high level of functioning, a high score for the global health status represents a high QoL, and a high score for a symptom scale represents a high level of symptoms or problems. Transformed scores and change from baseline for each scale will be summarized by timepoint, by cohort or schedule, and overall. By-patient listings will be presented for response assessments, including RECIST and GCIG results by visit (the best overall response will be flagged), investigator assessment of target and non-target lesions, and EORTC QLQ-C30 responses.

4.3.3.

[figure not shown]
CCI

CCI

Relevant Output

CCI

CCI

CCI

CCI

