##### Raw Score:

For all scales, the Raw Score (RS) is the mean of the component items, where I = Item:

- Raw Score:  $RS = (I_1 + I_2 + \dots + I_n)/n$

The items for each scale are identified in Table 4-4, Table 4-5, Table 4-6, and Table 4-7.

Transformed Score:

For each domain, the linear transformation is as follows:

- Functional scales:  $Score = \{1 - ((RS - 1)/range)\} * 100$
- Symptom scales / items and Global health status / QoL:  $Score = \{(RS - 1)/range\} * 100$

Range is the difference between the maximum possible value of RS and the minimum possible value. Most items are scored 1 to 4, giving range = 3. The exceptions are the items contributing to the global health status / QoL, which are 7-point questions with range = 6, and the initial yes/no items on the earlier versions of the QLQ-C30 which have range = 1.

Example: Emotional Functioning:  $RS = (Q21+Q22+Q23+Q24)/4$

$$EF \text{ Score} = \{1 - (RS-1)/3\} * 100$$

Missing Scores:

If less than half of the scores are missing for any domain, the remaining items will be used applying the standard equations given above for calculating the scale scores. If at least half of the scores are missing, the scale will be missing. For single item measures, the score will be missing.

Example: Q23 is missing

Emotional Functioning:  $RS = (Q21+Q22+Q24)/3$

$$EF \text{ Score} = \{1 - (RS-1)/3\} * 100$$

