**Table 4-6 EORTC QLQ-CX24 Scoring - Cervical Cancer Supplement**

Domain	Scale		Number of Items	Item Range*	Version 3.0 Item Numbers
Functional Scales	Body image	CXBI	3	3	15-17 (45-47 in eCRF)
	Sexual activity	CXSXA	1	3	19 (49)
	Sexual enjoyment	CXSXE	1	3	24 (54)
	Sexual/vaginal functioning	CXSV	4		20-23 (50-53)
Symptom scales	Symptom experience	CXSE	11	3	1-7, 9, 11-13 (31-37, 39, 41-43)
	Lymphoedema	CXLY	1	3	8 (38)
	Peripheral neuropathy	CXPN	1	3	10 (40)
	Menopausal symptoms	CXMS	1	3	14 (44)
	Sexual worry	CXSW	1	3	18 (48)

\* Item range is the difference between the possible maximum and the minimum response to individual items; most items take values from 1 to 4, giving range = 3.

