**Table 4-7 EORTC QLQ-EN24 Scoring - Endometrial Cancer Supplement**

Domain	Scale		Number of Items	Item Range*	Version 3.0 Item Numbers
Functional Scales	Sexual interest	ENSXI	1	3	49
	Sexual activity	ENSXA	1	3	50
	Sexual enjoyment	ENSXE	1	3	54
Symptom scales	Lymphoedema	ENLY	2	3	31-32
	Urological symptoms	ENUR	4	3	34-37
	Gastrointestinal symptoms	ENGI	5	3	38-42
	Poor body image	ENBI	2	3	47-48
	Sexual/vaginal problems	ENSXV	3	3	51-53
	Pain in back and pelvis	ENBP	1	3	33
	Tingling/numbness	ENTN	1	3	43
	Muscular pain	ENMP	1	3	44
	Hair loss	ENHL	1	3	45
Taste change	ENTC	1	3	46	

\* Item range is the difference between the possible maximum and the minimum response to individual items; most items take values from 1 to 4, giving range = 3.

CCI

Relevant Output

CCI

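### The SAP's reversed functional-scale formula, applied to the sexual interest, activity and enjoyment items, scores the best answer 0 and the worst 100

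*SAP*

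**What the plan says.** SAP section 4.3.2, item 5, codes the answers: "Each question is scored using a scale of 1 to 4, representing answers of Not at All, A Little, Quite a Bit, Very much". Only the global health items differ, running from 1 to 7. It then explains how to read the transformed scores. The general statement is "All of the scales and single-item measures range in score from 0 to 100, where a high score represents a higher response level", and for the functional domain it is "A high score for a functional scale represents a high level of functioning". Transformed scores and their change from baseline are to be summarised for each scale, by timepoint and cohort.

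Section 4.3.5 gives the scoring rule. It is set at domain level ("For each domain, the linear transformation is as follows"), with two formulas:

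- "Functional scales": {1 − ((RS − 1)/range)} × 100, the reversed form.
- Symptom scales and items, and global health status: {(RS − 1)/range} × 100, the direct form.

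RS is the mean of the component items, so for a single item it is the answer itself. The section refers to Tables 4-4 to 4-7 for the items of each scale, so the rule covers the disease modules as well as the QLQ-C30. It makes no exception for any item.

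Among the functional scales, Table 4-6 (cervical module) includes "Sexual activity" and sexual enjoyment. Table 4-7 (endometrial module) has sexual interest, sexual activity and "Sexual enjoyment". All five are single items with range 3.

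**The concern.** The reversed formula turns a low amount of a problem into a high score. It is right when the answer very much means more of a problem. For an item on sexual interest, activity or enjoyment, very much is, on the natural reading, the better state. Reversing it makes a high score mean low functioning, which contradicts the interpretation in section 4.3.2.

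A programmer who follows section 4.3.5 as written would produce inverted scores for these items. A reader who follows section 4.3.2 would take them at face value: in Cohorts B and C, a patient who loses enjoyment would appear to gain function, and the reverse. The summary table would not reveal this, because the values still lie between 0 and 100.

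**Working it through.** **Inputs**

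- Answer coding 1, 2, 3, 4 for not at all, a little, quite a bit, very much: SAP 4.3.2, item 5.
- Formulas: SAP 4.3.5, Transformed Score.
- Range 3 and one item per scale: Table 4-6 for CXSXA and CXSXE; Table 4-7 for ENSXI, ENSXA and ENSXE.

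**Reproducing the SAP's own example.** Section 4.3.5 scores Emotional Functioning as {1 − (RS − 1)/3} × 100. At RS = 1, 2, 3, 4 this gives 100, 66.7, 33.3, 0. The general functional formula with range 3 gives the same four values, so the example and the rule agree.

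**Applying both formulas to one of the five items**

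| Answer | RS | Reversed, {1 − (RS − 1)/3} × 100 | Direct, {(RS − 1)/3} × 100 |
|---|---|---|---|
| Not at all | 1 | {1 − 0/3} × 100 = 100 | 0/3 × 100 = 0 |
| A little | 2 | {1 − 1/3} × 100 = 66.7 | 1/3 × 100 = 33.3 |
| Quite a bit | 3 | {1 − 2/3} × 100 = 33.3 | 2/3 × 100 = 66.7 |
| Very much | 4 | {1 − 3/3} × 100 = 0 | 3/3 × 100 = 100 |

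In every row the two columns add to 100, so the score under the written rule is 100 minus the direct score.

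**Change from baseline**

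- Answer 2 to answer 4: reversed 0 − 66.7 = −66.7; direct 100 − 33.3 = +66.7.
- Answer 1 to answer 4: reversed 0 − 100 = −100; direct 100 − 0 = +100.

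The size of a change is right and its sign is wrong.

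**Which scales are affected.** Two in the cervical module and three in the endometrial module, five in all. The cervical module has no sexual interest item. The ovarian module's sexuality items (Table 4-5) sit in the symptom domain and are not reversed, so Cohort A is not affected.

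**Direction of the items.** The SAP does not print the questions, so the direction is inferred from its labels. In Table 4-7 the scales framed as difficulties are named that way (poor body image, sexual/vaginal problems) and are placed under symptoms. Interest, activity and enjoyment carry no such qualifier and are placed under function. Read with an answer scale from not at all to very much, a 4 then means the most interest, activity or enjoyment.

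**The case against.** The strongest objection is that the deciding premise is not in the documents: neither the SAP nor the protocol prints the wording of a single module item. Scale names are not a safe guide on their own. Physical, role, emotional, cognitive and social functioning all have positive names, yet the reversed formula is accepted for them. The cervical module also lists sexual/vaginal functioning (four items) and body image as functional, and nothing in the SAP settles their direction. If the five items were worded as problems, nothing would be inverted. This stands as a limit on certainty. It is weakest against interest and enjoyment, which are hard to read any other way on this answer scale. It has more force against activity, where treating more as better rests on the functional label.

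A second objection is that the SAP also points to the EORTC QLQ-C30 Scoring Manual and cites the module papers, and that redacted table shells might hold an item-level note. But the manual named is for the C30, section 4.3.5 writes its formulas out and applies them to all four tables, and no visible text makes an exception. Other text that might exist does not displace the written rule.

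A third objection is that little depends on it, and this is correct. Formal testing is confined to the primary endpoint (SAP 3.2). Protocol 8.4.3 and SAP 1.2.5.1 name only the QLQ-C30 as the quality-of-life measure, and its scoring is unaffected. An inverted score can be recovered exactly as 100 minus the reported value, provided someone notices.

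**Conclusion.** The concern holds. As written, section 4.3.5 gives five single-item scales (CXSXA, CXSXE, ENSXI, ENSXA, ENSXE) scores that run opposite to the meaning stated in section 4.3.2. The inversion is complete: each reported score is 100 minus the intended one, and every non-zero change from baseline has the wrong sign.

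This rests on one assumption, that the items ask in the direction of their names. The SAP's own division between functional and symptom scales supports it, but only the questionnaire text can confirm it.

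The consequence is minor: descriptive secondary sub-scores in Cohorts B and C. No hypothesis test, disease control result, general QLQ-C30 scale or ovarian module score changes. It is worth correcting because the error would mislead a reader and costs almost nothing to remove.

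**What to change.** First, check the wording of each single-item functional scale in Tables 4-6 and 4-7 against the eCRF before programming. The two multi-item functional scales in Table 4-6 can be checked at the same time.

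Then, for the items confirmed as positively worded, add one sentence to section 4.3.5: CXSXA, CXSXE, ENSXI, ENSXA and ENSXE are scored as {(RS − 1)/range} × 100. Answers 1 to 4 then score 0, 33.3, 66.7 and 100, and the reading given in section 4.3.2 holds for them.

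The cost is one line in the SAP and a short wording check. No data collection, sample size or other analysis changes.

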#### 4.3.4. GCIG Disease Assessment

Disease response per GCIG response criteria will be derived as defined in

Table 4-1 and in Appendices 12 through 14 of the study protocol.

If there was no measurable disease per RECIST at baseline, GCIG response is derived as presented in Table 4-2. If there was measurable disease per RECIST at baseline, GCIG response is derived as presented in Table 4-3. Date of response or progression is the date of the earlier of the 2 assessments (CA-125 or RECIST).

**Table 4-1 CA-125 Disease Response**

Response Category	Criteria	Additional information
Complete Response	50% reduction in CA-125 levels from a pretreatment sample. The value must also return to within normal range and be maintained for 28 days (i.e. <10% change between response and confirmation sample)	To have a response, the pre-treatment sample must be at least twice the upper limit normal range (ULN). The date when the CA-125 level is first reduced by 50% is the date of the CA-125 response.
Partial Response	50% reduction in CA-125 levels from a pretreatment sample that is maintained for 28 days, but result is not yet within normal range.	For a partial response, the CA-125 is not yet within normal range, the pre-treatment sample must be at least twice the ULN.
Normalized	CA-125 returned to within normal range, but was not twice the ULN at baseline	
Disease Progression	
Any of the following scenarios are categorized as PD.
 
For patients with CA-125 elevated at baseline:
 
 
- If CA-125 normalized (within normal range) at any point, then increases to twice ULN on 2 occasions at least 1 week apart, date of PD is when CA-125 was first measured at twice ULN.
 
- If CA-125 never normalizes (within normal range), then increases to twice the nadir value on 2 occasions at least 1 week apart, date of PD is when CA-125 was first measured at twice the nadir value.
 
 
For patients with normal CA-125 at baseline:
 
 
- If CA-125 increases to twice ULN on 2 occasions at least 1 week apart, date of PD is when CA-125 was first measured at twice ULN.
 
	
Non-PR/ Non-PD	None of the above are true	

